3.4. Cohort Characteristics and Eligibility

3.4.1 Patient Participants

Patients will be eligible if: 1) they are enrolled in COH IRB 07047, 2) have a cancer diagnosis, 3) they are having somatic, germline or paired somatic/germline sequencing, 4) they are fluent in English, 5) they have an ECOG performance status of 0-2, and 6) they are ≥ 18 years old.

Patients will be ineligible if they 1) are unable to provide informed consent.

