4.1.2 Patient Follow Up Survey

The follow up surveys will either be mailed to the participant, along with a return envelope, provided electronically and/or by text message via REDCap survey link, or completed via phone or Zoom call with a staff member, according to patient preference. For patients who opt to complete their follow-up surveys via phone or Zoom call, study staff will not assist them in selecting the correct answers for questions pertaining to their understanding of cancer and genetics. Study staff will follow-up with patients once a week within 2–3-week window to encourage completion of the survey. We will attempt to contact non-responders up to five times to encourage survey participation.

Understanding of personal genomic knowledge will be assessed through an adapted version of a measure created by Freedman and colleagues¹, which evaluated women's knowledge of their personal cancer ER and HER2 status using a two-item question (3 response options; yes/no/I don't know). Our adapted questions will evaluate patients' recall of genomic testing results and the implications of their results (i.e., harmful and unknown). Patient recall will be assessed at all survey timepoints (i.e., at baseline, 10 days, 3 months and 9-months following results disclosure with a clinician).

Engagement in care will be assessed by a novel item that queries patients as to whether WES prompted questions to care providers (yes, no, don't know). We will use items adapted for our CSERII study to ask patients if they recall changes to their cancer treatment as a result of their genomic test results. We will also assess engagement via interactive functionality of HOPE-Genomics (see below). Seeking and sharing information about genetic tests will be assessed using two items from the Health Information National Trends Survey (HINTS) 4 that were adapted for our CSERII study.⁷

Satisfaction with physician/patient communication around the results of gene testing will be assessed with a 7-item measure adapted from HINTS 3 & 4. Satisfaction with care will be assessed using a single item measure from Charles and colleagues that was created to evaluate satisfaction with genetic counseling and that was adapted for our CSER1 study.¹⁴ We have also included two novel questions to assess whether patients (1) recalled asking their healthcare providers about their genetic test results and (2) recalled receiving a copy of their genetic test report.

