6.2.1 Primary Outcome

In Aim 1, recall rates of personal genomic results at the 10-day post-disclosure timepoint for Arms 2 and 3 of the study will be pooled together so that the main comparison is a two-sample test of proportions between patients under usual care (Arm 1) vs. patients with any exposure to the HOPE-Genomics tool (Arms 2/3). Pilot studies indicate that a recall rate for patients with an actionable somatic finding are approximately 39% under usual care. An analytical sample of 390, assuming a 39% recall rate under usual care (Arm 1: n = 130) with a 15% improvement using the tool (Arms 2/3: n = 260), will be sufficient to detect a difference in proportions with 80% power and alpha = 0.05 (two-sided with no adjustment for multiplicity). Rates of recall will be analyzed using a two group Chi-Square test of equal proportions, and logistic regression when controlling for covariates such as age and education level. The overall fit of the model will be examined using Hosmer-Lemeshow goodness-of-fit test and ROC curves. If any normality issues arise, non-parametric techniques such as the Mann-Whitney test will be deployed. Recall rates will be defined as the number of participants who correctly recall somatic test results, which will be assessed in the second question of the 10-day post-disclosure survey.

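### Section 6.2.1 takes its 39% control recall rate from patients with an actionable somatic finding but applies it to all 390 analysed patients, so the 80% power depends on an unstated assumption about everyone else

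*Combined protocol and SAP*

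**What the plan says.** The planning rate is in section 6.2.1: "Pilot studies indicate that a recall rate for patients with an actionable somatic finding are approximately 39% under usual care". The next sentence carries it to the whole trial: "An analytical sample of 390, assuming a 39% recall rate under usual care (Arm 1: n = 130", and then "with a 15% improvement using the tool (Arms 2/3: n = 260", for "80% power and alpha = 0.05 (two-sided with no adjustment for multiplicity". Section 6.1 obtains the 390 from all 465 accrued patients less attrition, so it is not a subset chosen by result.

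The endpoint is given as a count with no denominator: "Recall rates will be defined as the number of participants who correctly recall somatic test results". The analysis is unstratified: "Rates of recall will be analyzed using a two group Chi-Square test of equal proportions". A logistic regression is added for covariates, with age and education as examples. Result type is not named.

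Nothing selects on a finding. Section 3.4.1 admits patients if "they are having somatic, germline or paired somatic/germline sequencing". Section 4.1 randomises immediately after enrolment. Section 6.1 anchors the cohort on somatic testing, which is not the same as an actionable result. The patient information in Appendix O says that testing may yield nothing helpful or may fail.

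**The concern.** The patients who supplied the 39% are not the patients who will be analysed. The analysed group will include people with no actionable somatic finding and, as eligibility is written, people with germline testing only. The plan gives no expected actionable share, no recall rate for the others, and no rule for scoring a negative or absent somatic result.

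Two things are at stake. First, if the tool adds less for patients with nothing actionable to recall, the overall difference shrinks below 15 points and the trial is weaker than stated. A null overall result could then hide a real gain among patients with a finding. Second, an overall recall rate cannot be set against the 39% benchmark, because it describes a different mix of patients.

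Correct recall may also be a different task when there is a finding to name than when there is none. This is an inference. Section 4.1.2 describes the source measure as having "3 response options; yes/no/I don't know", but the adapted item, the second question of the 10-day survey, is not shown.

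**Working it through.** **Inputs from section 6.2.1:** control rate 0.39; gain 15 points, read as absolute, so 0.54; n1 = 130; n2 = 260; two-sided alpha 0.05.

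**Formula (normal approximation to the chi-square test, no continuity correction):** with p̄ = (n1·p1 + n2·p2)/(n1 + n2),
- SE0 = √[p̄(1 − p̄)(1/n1 + 1/n2)]
- SE1 = √[p1(1 − p1)/n1 + p2(1 − p2)/n2]
- power = Φ[(|p2 − p1| − 1.96·SE0)/SE1]

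**Step 1: the plan's own figure.** p̄ = (130 × 0.39 + 260 × 0.54)/390 = 0.49. SE0 = 0.0537 and SE1 = 0.0528. Power = Φ[(0.15 − 1.96 × 0.0537)/0.0528] = Φ(0.848) = 0.802. The 80% is reproduced. Reading the 15% as relative (39% to 44.9%) gives 0.193, so the absolute reading is the intended one.

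**Step 2: change only the control rate and keep 15 points for everyone.**

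| Control rate | 0.20 | 0.30 | 0.39 | 0.50 | 0.60 | 0.70 | 0.80 |
|---|---|---|---|---|---|---|---|
| Power | 0.88 | 0.82 | 0.80 | 0.81 | 0.86 | 0.92 | 0.99 |

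A rate of 39% is close to the least favourable position, so a different rate by itself does no harm.

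**Step 3: let the gain differ.** Let f be the share with an actionable finding, q the control recall in the rest, and e the gain in the rest. Then p1 = 0.39f + q(1 − f) and p2 = 0.54f + (q + e)(1 − f), so the overall difference is 0.15f + e(1 − f). The values of f, q and e are assumptions; the documents give none of them. The range of q is 39% to 80%.

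| f | e | Overall difference | Power over the range of q |
|---|---|---|---|
| 0.75 | 5 points | 0.1125 + 0.0125 = 12.5 points | about 0.65 |
| 0.50 | 5 points | 0.075 + 0.025 = 10 points | 0.46–0.50 |
| 0.50 | none | 7.5 points | 0.29–0.31 |
| 0.50 | 15 points | 15 points | 0.80–0.85 |

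Worked row, f = 0.5, q = 0.39, e = 0.05: p1 = 0.39, p2 = 0.49, p̄ = 0.4567, SE0 = 0.0535, SE1 = 0.0528. Power = Φ[(0.10 − 0.1049)/0.0528] = Φ(−0.092) = 0.463.

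**Step 4: does stratifying recover the power?** Simulated power of the Cochran-Mantel-Haenszel test against the unstratified chi-square test:
- f = 0.5, q = 0.39, no gain in the rest: about 0.29 for both.
- f = 0.5, q = 0.80, 5-point gain in the rest: about 0.56 against 0.50.

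It was never lower in the scenarios tried and helps when recall differs between strata. It does not restore 80%.

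**Step 5: germline-only patients, share g (assumed).** At g = 10% and 20%, scoring them as incorrect gives power of 0.72 and 0.63. Excluding them gives 0.76 and 0.71.

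**The case against.** The strongest reply is that the plan ties only the 39% to actionable patients. The 15-point improvement is stated for the analysed sample as a whole, and on that basis the 80% is correct. This stands. A reader might infer from the mismatch that the trial is underpowered, or that the 15-point gain was derived in actionable patients. The documents support neither reading: step 2 shows that a different control rate alone leaves power at or above 0.80, and the losses in step 3 come only from assumed smaller gains.

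A reader might also infer that patients with nothing actionable answer correctly by default in every arm. That does not follow either. The item is not shown, the three response options are given for the source measure, and an uninformed patient could choose the don't-know option. Nor do the documents say that the tool helps mainly patients with a finding, since it returns results to everyone in Arms 2 and 3.

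The unstratified chi-square test is a valid test of the overall effect under randomisation. The regression covariates in 6.2.1 are open-ended, and section 4.6 already abstracts somatic biomarker testing. That makes the change easy, but no text commits to using result type.

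**Conclusion.** The mismatch between the population behind the 39% and the population analysed is real, and no other section resolves it. It does not show that power is below 80%. It shows that the 80% is conditional on a 15-point gain across all 390 patients, including those with no actionable finding, and that the plan does not say so. If the gain in those patients is 5 points, power is about 0.65 at a 75% actionable share and 0.46 to 0.50 at 50%. With no gain in them it is about 0.29 to 0.31 at 50%. These are illustrations under assumed shares and gains, with control recall of 39% to 80% in the rest.

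Interpretation is affected whatever the true share: without stratum results, the overall rate cannot be compared with the pilot figure. This should be corrected, but it does not invalidate the primary test.

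**What to change.** Keep the sample size and the pooled contrast of Arms 2/3 against Arm 1, and amend section 6.2.1 as follows.

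1. Analyse recall with a Cochran-Mantel-Haenszel test, or a logistic model, stratified by somatic result type from the laboratory report (actionable finding or none). Allocation cannot affect this variable. Define actionable, and say where uncertain results fall, before outcome data are examined.
2. Report the risk difference in each stratum, and compare only the actionable stratum with the 39% pilot rate. State that the stratified test does not itself rescue power when the effect is confined to one stratum; the stratum estimates are what show such a pattern.
3. Limit the recall denominator to patients with a somatic result, since germline-only patients have none to recall. If that leaves fewer than 390, recompute the power.
4. State that 80% power holds only if the 15-point gain applies across all 390 patients, and give the range above as illustrative.

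The cost is a power statement that becomes conditional and the coding of result type from laboratory data that section 4.4 says the study will store. No extra patients or survey items are needed.

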4.1.1 Patient Baseline Survey

At time of consent, patients will complete the baseline survey. Baseline survey outcomes are detailed in Table 1. We will follow standard survey methods as outlined by Dillman^{2,3} (e.g., contact type and intervals; mail/email/in-person reminders) to ensure high response rates. The survey will be administered in one of the following ways, according to patient preference: (1) mailed to the participant, along with a return envelope, (2) provided electronically and/or by text message via REDCap survey link, or (3) completed over a scheduled phone or Zoom call with a study staff member. For patients who complete the baseline survey via phone or Zoom call, study staff will not assist them in selecting the correct answers for questions pertaining to their understanding of cancer and genetics.

Germline sequencing knowledge will be measured using an adapted version of the UNC Genomics Testing Knowledge Scale¹, a validated 25-item measure developed by Langer and colleagues to evaluate overall understanding of genomics and health. We will also assess patients' knowledge of the implications of WES on 1) personal cancer risk, 2) family cancer risk, and 3) genetics generally.

General cancer genomics knowledge will be assessed using a modified form of a 12-item measure developed by Blanchette and colleagues.⁵ The measure assesses three domains of cancer genomic knowledge: 1) general understanding of cancer, 2) how biological changes influence cancer, and 3) the potential implications of genomic testing in cancer. Higher general cancer genomic knowledge has been associated with higher levels of education, higher personal income and patients' perceived ability to provide informed consent for genomic testing.

Knowledge about the use of genetic testing in cancer will be assessed using a 6-item measure developed by Roth, Gray and colleagues for the Lung-MAP study (unpublished). The measure assesses participant's knowledge of why genetic testing is used in cancer care (e.g., to help select a treatment, to predict response to treatment). Eight items have been added in the following content areas: 1) use for cancer staging, 2) use to time cancer onset, 3) use to predict treatment efficacy, 4) use for clinical trials, 5) use to monitor cancer treatment, 6) use to identify a cancer's location, 7) use to determine metastasis, and 8) use to assess cancer risk.

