Other covariate data (e.g., health literacy, numeracy, health status, and primary language spoken) will be assessed using validated measures.

- Health literacy will be assessed by up to 3 single-item health literacy screening questions, as evaluated by Chew and colleagues.⁵
- Numeracy will be assessed by a 3-item version of the Subjective Numeracy Scale (SNS-3), as validated by McNaughton and colleagues.¹⁷
- Health-related Internet use will be assessed by a an adapted 1-item measure from the National Cancer Institute Health Information National Trends Survey (HINTS).^{18,19}
- Health status will be assessed by a validated single item measuring general self-rated health.^{18,20,21}
- Patient-reported functional status will be measured by a single item measure developed by Basch and colleagues (patient ECOG-PS).²²
- Quality of care will be assessed using a single item measure from HINTS.⁶

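### The deciding test of 10-day recall is unadjusted, and the baseline knowledge and literacy scores that could sharpen it are collected but not prespecified

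*Combined protocol and SAP*

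**What the plan says.** Section 6.2.1 (Primary Outcome) states that "the main comparison is a two-sample test of proportions between patients under usual care (Arm 1" arm) and the pooled Arms 2 and 3. The design figures are tied to that comparison: "assuming a 39% recall rate under usual care (Arm 1: n = 130"), "with a 15% improvement using the tool (Arms 2/3: n = 260"), and "80% power and alpha = 0.05 (two-sided with no adjustment for multiplicity").

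On method it says: "Rates of recall will be analyzed using a two group Chi-Square test of equal proportions", followed by "logistic regression when controlling for covariates such as age and education level". The covariates are given as examples. The section gives no closed list, no functional form, no rule for missing covariates, and no explicit statement of which result prevails if the two analyses differ.

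Section 6.2 says in general terms that the survey, demographic and clinical data will serve for covariate adjustment, without specifying a model.

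Section 4.1.1 (Patient Baseline Survey) describes several baseline knowledge instruments, including a 12-item general cancer genomics measure. On literacy it says: "Health literacy will be assessed by up to 3 single-item health literacy screening questions"; these items are introduced as covariate data. On knowledge it notes: "Higher general cancer genomic knowledge has been associated with higher levels of education". Neither knowledge nor literacy is named in Section 6.2.1.

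**The concern.** An unadjusted test of a binary outcome makes no use of what is known about each patient at baseline. If baseline knowledge or health literacy predicts whether a patient recalls the somatic result, adjusting for it raises power at the same sample size and guards against chance imbalance between arms. The analysed sample of 390 is set at almost exactly the 80% target, so a few points of power are worth having. The items are already in the baseline survey.

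There is also a smaller gap in specification. Two analyses of one endpoint are listed, one with an open covariate list. The text leans clearly towards the chi-square but does not say that the logistic result is only supportive. If the two disagreed, the plan would not settle the matter in so many words.

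**Working it through.** **1. Inputs from Section 6.2.1.** Recall 39% vs 54% (39% plus 15 points), n = 130 vs 260, two-sided alpha 0.05.

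**2. Reproducing the stated power (pooled variance, no continuity correction).**

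- Pooled rate: (130 × 0.39 + 260 × 0.54) / 390 = 191.1 / 390 = 0.49
- SE under the null: √[0.49 × 0.51 × (1/130 + 1/260)] = 0.0537
- SE under the alternative: √[0.39 × 0.61/130 + 0.54 × 0.46/260] = 0.0528
- Power: Φ[(0.15 − 1.96 × 0.0537) / 0.0528] = Φ(0.848) = 80.2%

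The stated 80% at N = 390 reproduces.

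**3. Power with adjustment, by formula.** Let R² be the share of outcome variance explained by the baseline covariates. The documents give no value, so a range is assumed. The effective sample size is 390 / (1 − R²), entered in the formula of step 2.

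| Assumed R² | Effective N | Power |
|---|---|---|
| 0 | 390.0 | 80.2% |
| 0.02 | 398.0 | 81.0% |
| 0.05 | 410.5 | 82.2% |
| 0.10 | 433.3 | 84.2% |
| 0.15 | 458.8 | 86.2% |
| 0.20 | 487.5 | 88.2% |

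**4. Check by simulation.** 6,000 trials per setting, 130 vs 260, marginal rates fixed at 39% and 54%, one normally distributed baseline score, Wald test of arm in the adjusted logistic model against the chi-square.

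| Log-OR per SD | R² | Chi-square | Adjusted logistic | Gain (points) |
|---|---|---|---|---|
| 0 | 0 | 79.7% | 79.7% | 0 |
| 0.3 | 0.021 | 79.8% | 80.7% | 0.9 |
| 0.5 | 0.055 | 80.3% | 82.4% | 2.1 |
| 0.75 | 0.110 | 79.6% | 84.7% | 5.1 |
| 1.0 | 0.171 | 79.3% | 86.8% | 7.5 |

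The Monte Carlo standard error is about √(0.8 × 0.2 / 6000) = 0.5 points. With no arm effect, type I error was 4.2% to 5.4% for both tests.

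**5. Price of useless covariates.** With four covariates of no prognostic value (5,000 runs), power was 80.0% adjusted and 80.2% by chi-square, which is no material loss.

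**6. If either p-value could be used.** With 39% in both groups (5,000 runs, standard error about 0.3 points), claiming success on either the chi-square or a four-covariate logistic model gave type I error of 6.6%, 6.3% and 7.0% at log-OR 0.5, 0.8 and 1.0 per SD. At 39% vs 54%, the two tests disagreed on significance in 5%, 9% and 10% of trials.

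**7. Missing baseline items.** Dropping incomplete records works against the gain. At R² = 0.05, a 5% loss leaves 390 × 0.95 / 0.95 = 390 effective patients, which cancels it.

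**8. Which knowledge score.** Section 4.3 has Arm 3 view the tool before completing the pre-education survey, so in that arm the survey is a post-intervention measure. The baseline survey is completed at consent, and Appendix G sends the Arm 3 tool invitation to patients who have completed their first survey. Only the baseline score is suitable for adjustment.

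**The case against.** The best case for leaving the plan alone is that Section 6.2.1 calls the two-sample test of proportions the main comparison, bases the power on it, and names the chi-square first. The natural reading is a chi-square with an adjusted companion, and the chi-square does what the plan claims. Preferring an adjusted test is then a judgement about efficiency. This stands, and it limits the point to an improvement.

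Several stronger readings are tempting, and the documents do not support them:

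- **That the baseline data are left unused.** The covariate list is open and already names age and education, Section 6.2 foresees covariate adjustment, and Section 4.1.1 labels literacy as covariate data. The accurate statement is that knowledge and literacy are not prespecified for this analysis.
- **That adjustment is certain to raise power.** No section gives the prognostic strength of knowledge or literacy for recall of a patient's own somatic result. The cited link is between knowledge and education, which is already an example covariate, so the gain beyond education may be smaller.
- **That the design has no reserve.** Section 6.1 accrues 465 with 10% attrition, which is 465 × 0.90 = 418.5 and not 390. At about 418 the unadjusted power would be 82.9%. The two figures conflict, so the margin cannot be stated flatly.
- **That type I error is inflated as the plan stands.** The 6 to 7% arises only if success may be claimed on whichever p-value is smaller, and the plan does not say so.

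It is also fair to object that a baseline genomic knowledge score is not a single variable here. Section 4.1.1 has several instruments, and Section 6.0 foresees item reduction and an amended survey. The fix must therefore name one scale.

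**Conclusion.** The point holds as a worthwhile improvement. The unadjusted chi-square is valid and has 80.2% power under the plan's assumptions, so neither the sample size nor the planned test is wrong. What is missing is a prespecified covariate set that uses the baseline scores, and an explicit statement of the one analysis that decides.

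The size of the gain is conditional: about 0 points of power if the covariates do not predict recall, about 2 at 5% of outcome variance explained, 4 to 5 at about 11%, and 7 to 8 at 17%. These variance shares are assumptions. The figures also assume that patients with missing baseline items stay in the model. Naming one test removes the possibility of a 6 to 7% type I error from a choice between two p-values, whatever the covariates turn out to explain.

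**What to change.** Amend Section 6.2.1 as follows:

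- Name one deciding analysis: a logistic model of 10-day recall on arm (Arms 2/3 vs Arm 1), with the test of the arm coefficient as the single deciding p-value.
- Close the covariate list: one named baseline knowledge scale (for example the 12-item general cancer genomics measure, as finalised), health literacy, age and education, each with its functional form.
- Take the knowledge score from the baseline survey only, not from the pre-education survey.
- State a simple rule that keeps patients with missing baseline items in the model, for example imputation from baseline data without reference to arm or outcome.
- Report the risk difference standardised over the analysed sample, which keeps the 15-point scale of the design.
- Keep the chi-square as a supporting analysis.

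If the sponsor prefers the chi-square as the deciding test, saying so and closing the covariate list would settle the choice between p-values but forgo the possible gain in power.

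The cost is SAP wording, slightly more analysis work and the handling of missing baseline items. No new data, visits or patients are needed.
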